**Part B: Experimental Design and Protocol – ALL APPLICANTS MUST COMPLETE THIS FORM**

All investigators must submit a completed Part B with their New Protocol or Continuing Review application. If a protocol from a corporate sponsor or cooperative group is available, this must also be submitted.

Each question in Part B should be answered thoroughly with answers that are specific to how the research will be conducted at Children's Hospital, Boston.

Do not cut and paste from the protocol or from a grant application to complete Part B. Instead, complete each question in Part B by referencing the applicable page and section number of the protocol which answers the questions in Part B. For some questions in Part B, such as those regarding recruitment methods, confidentiality provisions, and adverse event reporting, you will need to provide complete answers rather than references to the protocol, since the protocol will not address these items as they apply specifically to how the research will be conducted at CHB.

Further information may be obtained by referring to [the policies and procedures on the CCI website](#)

## **1. Abstract**

This research protocol describes a randomized control trial to compare two different methods of managing home oxygen therapy in premature infants. This is a multicenter study involving 9 centers. We plan to enroll a total of 196 infants, of which 68 will be from Boston Children's Hospital (BCH). The current standard for oxygen management includes brief assessments of a patient's oxygen saturation status during monthly clinic visits. The patient's oxygen status between visits is assumed to be acceptable; although it is possible for significant hyperoxia or hypoxia to occur, providers have no data to help with decision-making. In many centers, final steps before discontinuing home oxygen therapy (HOT) often include polysomnography (PSG), which can be costly and requires the inconvenience of rehospitalization. Advances in data storage and pulse oximetry technology have expanded potential uses for recorded home oximetry (RHO) in the accurate assessment of hypoxemia. At Boston Children's Hospital, we have pioneered the use of recorded home oximetry (RHO) in other research protocols, and shown that it can be a simple and convenient method for parents to transmit oximetry data to providers.

In this trial, we will randomize premature infants who require HOT at time of discharge from the NICU, who are referred for follow-up at the Center for Healthy Infant Lung Development. At the time of their first outpatient appointment, infants will be randomized to one of two treatment arms:

**Arm A (“Standard therapy”):** Infants' oxygen will be increased, decreased, or maintained based on brief structured assessments during monthly clinic visits. Polysomnograms will be utilized prior to final discontinuation of oxygen. RHO will only be utilized on the night prior to and during the polysomnogram to compare these two modalities.

**Arm B (RHO):** Infants will have the same monthly clinic assessments as in Arm A, but also will utilize RHO to potentially increase, decrease or maintain oxygen between monthly visits. Parents will transmit a minimum of 25 hours (1500 minutes) of stored RHO data (approximately 4 days, 8 hours per day) every 4-7 days. Changes in oxygen needs will be made based on standardized objective criteria. To determine discontinuation of oxygen, RHO will be utilized instead of polysomnography.

Parents of all infants will be asked to complete a structured quality-of-life survey, the PedsQL Family Impact Module (PedsQL), at their initial (baseline) clinic visit, and monthly at each clinic visit until the infant is weaned. A follow-up PedsQL will be done 3 months after weaning either by phone or at a clinic visit. Health care utilization (emergency department visits and rehospitalizations) and information on growth and nutrition will be assessed at monthly clinic visits while the child is on oxygen, as well as 1 and 6 months after discontinuation of oxygen. Additionally, post-wean, but before their 6 month follow-up, parents of Arm B children will be approached in clinic, or contacted via phone, to collect a brief, 5 minute Home Oximetry Feasibility Questionnaire survey that helps to identify variables that may correlate with an increased or decreased likelihood to record and send home oxygen data.

Our overall objective is to determine whether RHO can improve caregiver quality of life, and can shorten HOT duration and eliminate need for PSG, without compromising safety. We will determine respiratory-related re-hospitalizations, emergency department (ED) visits, and growth parameters to confirm safety of the proposed weaning strategies.

Our specific aims include: **Specific Aim 1:**

**To evaluate the impact of a data-driven HOT management protocol on duration of HOT.** *We hypothesize that RHO will shorten duration of HOT therapy compared to the current standard HOT management protocol* **Specific Aim 2: To evaluate the effects of a data-driven HOT management protocol on parent quality of life.** *We hypothesize that RHO utilization will decrease emotional and financial stress compared to standard oxygen management approaches.*

**Specific Aim 3:**

**To evaluate the extent to which a data-driven HOT management protocol can improve growth and respiratory outcomes.**

*We hypothesize that RHO utilization will not increase rates of respiratory-related re-hospitalizations and ED visits, and will not impair growth compared to standard oxygen management protocols.*

## **2. Background and Significance**

Improvements in neonatal intensive care have led to increased numbers of premature infants surviving with chronic lung disease, including requirement for supplemental oxygen (O2). Current estimates indicate that over 50,000 premature infants are currently discharged home on supplementary O2 each year. At Boston Children's Hospital's Center for Healthy Infant Lung Development, we currently wean approximately 60-70 premature infants from home O2 annually.

Consensus guidelines for safe management of HOT do not currently exist. Current strategies to manage outpatient HOT include arbitrary timing of decreasing O2 delivery to lower flow rates prior to discontinuation, leading to potentially unnecessarily longer duration of HOT. The final step before completely discontinuing HOT often includes polysomnography (PSG), but the cost and inconvenience of this tool has led to a search for alternative strategies. PSG requires readmission to the hospital, and is relatively expensive. ***Inappropriate extension of HOT due to inefficient oxygen management strategies and use of potentially unnecessary, expensive weaning procedures both expose patients to potential toxicities and result in excessive cost to the health care system.***

In an effort to provide insight into resource utilization targets and best-practice guidelines, we performed a systematic review of the published clinical evidence. Surprisingly, we noted that guidelines exist but without any evidentiary basis. We then undertook a survey to identify best practice from the twenty top pulmonology programs in the country. Many providers rely on brief outpatient assessments of O2 status in monthly outpatient clinic visits to assume oxygenation status in the subsequent month. Prior to discontinuing O2, a majority of providers perform some form of nocturnal oximetry assessment, but there is no consensus on whether to perform the more expensive PSG versus inpatient or outpatient recorded oximetry.

The Center for Healthy Infant Lung Development (CHILD) program at Boston Children's Hospital (BCH) is one of the largest programs dedicated to the respiratory health of premature infants in the country. Through our extensive experience in clinical care of these patients, and through our experience in multicenter research collaborations, we have identified *recorded home oximetry* (RHO) as a potentially efficient, relatively inexpensive alternative tool to potentially save cost and improve the process of HOT management. RHO can provide extended O2 saturation data during the outpatient weaning process, and also provides data comparable to the more expensive PSGs that have been more recently encouraged.

[figure not shown]
Based on these analyses above, several conclusions could be drawn regarding local and national HOT management practices: 1) Variability in O2 weaning practice results in great variability in cost, 2) There is no evidence that more expensive O2 management strategies are either safer or more efficient, and 3) Evidence-based practice guidelines for clinical decision-making and optimal resource utilization are currently lacking.

## **3. Preliminary Studies/Progress Report**

Several preliminary studies have provided the basis for this proposed study.

Current HOT management strategies lack evidence for safety or efficacy. Our survey of US pulmonologists revealed striking variation in practice for weaning O2 therapy in infants with BPD. The majority of pediatric pulmonologists at major academic institutions rely on a combination of findings to aid them in establishing appropriate oxygen management practices for their patients. However, many of these practice determinants have never been prospectively studied or shown to actually predict safe discontinuation of O2 therapy. Consistent and practical methods need to be determined and integrated into the care of these formerly premature infants. Such a consensus is lacking in published clinical practice guidelines.

These findings are consistent with other reports from Europe and Australia.

Expensive, inconvenient diagnostic testing is more common without substantial evidence for improved safety or efficacy. Recent studies have investigated the role of overnight polysomnography (PSG) in HOT management. PSG has been recommended by some as a more accurate test for assessing pulmonary reserve and for determining the appropriate timing for weaning of supplemental oxygen in preterm children with CLD. There is little data to support the routine use of PSGs to manage supplemental oxygen needs in this population. Although there seems to be true equipoise regarding appropriate O2 management methods, the methods have very different emotional and financial impacts on families. The discomfort of hospital admission for PSG for disabled patients and their families has been well-described, while Marcus described PSG studies as time-consuming, disruptive to families' lifestyle, expensive and not always feasible because of the limited number of sleep laboratory facilities. **These studies support the need to evaluate more family-friendly, cost-efficient and safe alternatives to PSG.**

Simple, noninvasive methods of home oximetry data collection have been developed. We have completed pilot studies utilizing recorded home oximetry, which confirm feasibility of recording in the home, with accurate results. In one such study to assess intermittent hypoxia in former preterm infants, we recorded over 25,974 hours of analyzable recording from a total of 95 infants using the Masimo Rad-8 pulse oximeter interfaced with an Acumen serial data recorder, including recording in both the hospital and home. We have verified that simple, valid and time-saving strategies for automated software-based analyses can efficiently identify saturation parameters that can be used for clinical interpretation (accepted manuscript under revision, JAMA-Pediatrics).

In a separate study, we have identified reference values for nocturnal oximetry for use to identify readiness to wean from supplemental O2, which serve as the basis for the oxygen management protocol described in Table 1. In a population of 130 preterm infants weaned from HOT in our clinic, we have also determined the mean duration (144 +/- 66 days) of HOT (Manuscript in preparation). **The proposed study will build on these findings and methods and take this work in important new directions.**

## **4. Design and Methods**

### ***4a. Study Design***

We plan a prospective, multicenter, randomized trial of premature infants who require HOT. We will follow infants, beginning at the time of their first outpatient pediatric pulmonary appointment and continuing until 6 months from discontinuation of HOT. Duration of HOT therapy for each arm of the study will be documented by each site investigator. Questionnaires throughout the HOT managing process and after oxygen discontinuation will assess the impact of each HOT managing process on the parent quality of life. Growth assessments throughout of the HOT managing process and after oxygen discontinuation will track safety of both protocols. Similarly, assessment of health-care utilization (respiratory-related emergency department visits or rehospitalizations) at 6 months after discontinuation of HOT will track safety as well.

### ***4b. Patient Selection and Inclusion/Exclusion Criteria***

This study will focus on premature infants with chronic lung disease of prematurity, or bronchopulmonary dysplasia (BPD). This population makes up the largest group of children that require supplemental O2 and have an improving course that allows subsequent weaning. The results of our study will have more generalizability to several other populations (including both children and adults) that can wean from O2, as standardized protocols to wean O2 in those populations similarly do not exist.

Our intent is to select a representative target population of families of preterm infants with BPD that optimizes generalizability to preterm populations in general. Infants with conditions that may influence prolonged need for oxygen beyond lung disease of prematurity will be excluded.

Eligible parents will be recruited sequentially.

#### **Inclusion Criteria:**

Eligible parents will be:

- (1) parents of an infant with birth gestational age  $\leq 37$  (37 0/7) wks postmenstrual age (PMA) who has requirement for supplemental O2 at time of NICU discharge, as determined by primary NICU team.
- (2) parent of a child receiving pediatric pulmonology care at the Center for Healthy Infant Lung Development.
- (3) parent aged 18 years or older.
- (4) English or Spanish-speaking. (Spanish instruments will be developed through translation services and a Spanish-speaking interpreter will assist with interviews as needed to allow participation of potential Spanish-speaking families).

#### **Exclusion Criteria:**

Ineligible parents will be:

- (1) parents whose infants has presence of pulmonary hypertension at enrollment.
- (2) parents whose infant with syndrome or other diagnosis with known high risk for persistent hypoxia (cardiac disease, Trisomy 21, Pierre-Robin Sequence, etc.).
- (3) parents whose infant has requirement for O2 flow rate  $> 1$  L/min or tracheostomy
- (4) any infants who also require caffeine at discharge from the NICU. One parent per child will be eligible. Parents will be asked to respond to a question about which parent takes primary responsibility for daily monitoring of the child; the primary caregiver will be the eligible parent for each family. If the child's parents share care-giving responsibilities equally, then parents may choose which parent will participate.

#### **4c. Recruitment Methods**

This is a multi-center study. [name] is the Principal Investigator at University of Massachusetts Medical Center (UMass)).UMass Medical Center will act as the coordinating center. The other sites include, Boston Children's Hospital (PI: [name]) Baystate Medical Center (PI: [name]), UConn Medical Center (PI: [name]), University of Vermont Medical Center (PI. [name]), Dartmouth-Hitchcock Medical Center (PI: [name] [name]), Tufts Medical Center (PI: [name]), Boston Children's Hospital Physicians (PI: [name]) and Kentucky Children's Hospital, University of Kentucky (PI: [name] [name])

At BCH, potential eligible patients will be identified through one of two potential mechanisms: (1) identification of infants approaching readiness for discharge who will require supplemental home oxygen therapy (HOT) from Brigham and Women's Hospital (BWH) NICU or Beth Israel Deaconess Hospital (BIDMC) NICU or (2) identification of infants who present at their first outpatient appointment to the Center for Healthy Infant Lung Development (CHILD Clinic).

The site PI will review the NICU census at BWH and BIDMC once per week to identify infants who are approaching discharge and will require HOT, and to determine if there are contraindications to approaching families. They will then provide information about the study to parents in the NICU.

For infants who are eligible but not able to be approached due to logistics, or infants who are eligible but were discharged from other NICUs, the first provision of information will be at the first CHILD Clinic visit in their clinic room.

We will provide fliers to local referring NICUs to distribute to patients who will be discharged home on oxygen. These fliers will include contact information for study staff so that families may proactively ask questions or learn more about the study prior to their first clinic visit.

Subject recruitment will be performed by a team of research assistants in the study.

#### **4.d. Description of Study Treatments or Exposures/Predictors**

All participants will have the following study treatments:

1. Parents of enrolled infants will have parent reports/surveys to assess quality of life using the **PedsQL** at each monthly clinic visit until the infant has weaned and a 3 month post weaning follow-up PedsQL report/survey either by phone or in clinic.
2. All infants will have **growth assessments** at each monthly clinic visit before and after the wean.
3. **Nutrition regimen** will also be collected at each monthly clinic visit, and the 1 month and 6 month post-wean follow-up visits to capture factors that contribute to growth. Nutrition information will include any note on nutrition regimen made by a physician or nutritionist at the time of visit.
4. All infants will have **monthly clinic visits** with O2 challenges in clinic until oxygen is discontinued. (\*\*This is standard clinical care and not a separate research treatment)
5. Infants in Arm A ("Standard" management) will have **polysomnogram** performed prior to discontinuation of HOT. (This is a clinically-indicated, although not mandatory test). They will have RHO on the night prior to and during the polysomnogram.
6. Infants in Arm B (RHO) will use an **additional oximeter to record data** and will transmit the data every 4-7 days to research staff.
7. Parents of infants in ARM B (RHO) will also be given a **post study Home Oximetry Feasibility Questionnaire** to complete. This is a questionnaire that will be used to determine the advantages and challenges of using home oximetry. This questionnaire would be conducted at the 1 month post-wean visit, however, if unable to obtain at this time point, due to missed visit or lost to follow-up it can be collected post wean at any time at a clinic visit or over the phone.

*\*For patients in ARM B who have completed the study and have not completed the Home Oximetry Feasibility Questionnaire, this will be obtained from the parents retrospectively by sending them a letter and the questionnaire or by calling and obtaining verbal consent to conduct the questionnaire before doing so. Additionally, for all past patients, nutrition notes will also be obtained for the clinic visits that they attended during the course of the study.*

#### **4.e. Definition of Primary and Secondary Outcomes/Endpoints**

Primary measures: (a) Total duration of home oxygen therapy (HOT) from the first outpatient pulmonary appointment to discontinuation of supplemental O2; and (b) Parent quality of life, assessed by differences in the post-weaning PedsQL baseline.

Secondary measures: (a) Number of rehospitalizations and emergency department visits from 1st clinic visit through 6 months after discontinuation of HOT; (b) Change in weight and weight-for-length z-score from 1st clinic visit to 6 months after discontinuation of HOT; and (c) For patients who will receive a sleep study, percent time below designated O2 saturation thresholds (<96%, <93%, and < 90%) will be calculated from both RHO and from the polysomnogram data. The number of desaturation events (defined as saturation drops below 90% for >10 seconds and > 20 seconds) will also be analyzed.

Duration of HOT was chosen as a primary outcome since it is the primary driver of caregiver emotional and financial health for families of infants on HOT. This outcome was driven by input from families themselves, through a process of including important stakeholders in the protocol development process. The PedsQL was chosen as an additional primary outcome because it is validated, accurate scale in which scores correlate with maternal psychiatric symptoms, poor child health, poor child adjustment, and increased child hospitalizations.

This protocol focuses on patient-centered outcomes that may demonstrate non-inferiority from a medical safety perspective, but may improve quality of life. While families place a priority on treatment strategies that optimize health, when there are multiple choices without a clear medically superior choice, then the impact of specific treatment choices on quality of life will help drive decision-making.

Although our primary outcomes focus on quality of life, the secondary outcomes were chosen to confirm that weaning strategies (that likely improve quality of life) are not less safe. Assessment of short-term outcomes after discontinuation of therapies may miss significant later morbidities. We therefore included clinically relevant secondary outcomes at 6 months post discontinuation of O2 to assess the safety of the weaning strategies. Inadequate O2 supplementation has been associated with poor somatic growth, so growth parameters are an important outcome to confirm long-term safety of all studied weaning protocols. Higher O2 target saturations, with subsequent increased exposure to supplemental O2, have been linked to increased numbers of respiratory exacerbations. We therefore are also including rates of respiratory-related emergency department visits and rehospitalizations as additional secondary outcomes.

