**d. Statistical Power and Sample Considerations**

*Analyses for Aim 1:*

Aim 1: To evaluate the effects of a data-driven HOT management protocol on parent(s) quality of life.	Hypothesis 1.1: Parents of patients weaned from HOT using a data-driven management protocol will have improved quality of life compared to their status at time of NICU discharge compared to patients weaned using the current standard HOT management protocol.
--	--

For the impact of oxygen management protocol on the family's emotional health, we will use the PedsQL. We are performing these scales at the beginning of the outpatient HOT management process, to establish a baseline, and then will repeat these measures at the end of the HOT weaning process (6 months after discontinuation of HOT). We will test the association of oxygen management protocol with change in each measure using the Student's *t*-test to analyze the difference between intervention groups. Multivariate linear regression models will adjust for potential confounding variables, including parent and medical attributes.

Power calculation for hypothesis 1.1:

Power calculations are based on the primary analyses (t-test). A sample size of 130 will give 80% power, with 0.05 two-sided type I error rate, to detect a 20% absolute difference in emotional role limitation on the PedsQL, which we consider to be clinically significant.

*Analyses for Aim 2:*

Aim 2: To evaluate the impact of a data-driven HOT management protocol on duration of HOT.	Hypothesis 2.1: A data-driven HOT protocol will shorten duration of HOT therapy compared to the current standard HOT management protocol.
---	--

For the primary outcome, duration of HOT, the interval from date of first outpatient clinic visit/enrollment to discontinuation of HOT will be determined. Mean duration of HOT between the two groups will be compared.

Based on our experience weaning over 130 premature infants from O2, we expect the mean duration of HOT in our standard treatment group (clinic-based weaning) to be 144+/-66 days, and we anticipate that RHO weaning strategies will decrease the median duration by 25% (36 days) to 108 days. A total sample of 98 infants per group provides 97% power to detect this effect of the RHO strategy (two-tailed, alpha=0.05, see Table 2).

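### Two primary outcomes are each tested at two-sided 0.05 with no testing order, adjustment or joint-success rule, so the chance of a false primary claim exceeds 5% if success on either one counts.

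*Combined protocol and SAP*

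**What the plan says.** Section 4.e names two primary measures. The first is "Primary measures: (a) Total duration of home oxygen therapy (HOT", counted from the first outpatient pulmonary visit to the end of supplemental oxygen. The second is parent quality of life, and the section adds: "The PedsQL was chosen as an additional primary outcome".

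Section 5d gives each outcome its own power statement at full alpha:

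- PedsQL: "A sample size of 130 will give 80% power, with 0.05 two-sided type I error rate", sized "to detect a 20% absolute difference in emotional role limitation on the PedsQL".
- Duration: 98 infants per group "provides 97% power to detect this effect of the RHO strategy (two-tailed, alpha=0.05, see Table 2".

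Sections 5c and 5d contain no alpha split, testing order, multiplicity procedure or rule that both outcomes must succeed.

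On which outcome leads, the text points both ways. Section 1 makes duration Specific Aim 1 and quality of life Aim 2. Section 5d reverses this with "Aim 1: To evaluate the effects of a data-driven HOT management protocol on parent(s) quality of life", yet in its Aim 2 text it refers to duration, in the singular, as the primary outcome. Section 4.e lists duration as (a), but later says that the primary outcomes focus on quality of life.

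**The concern.** Each power statement implies a 5% false-positive risk. That figure belongs to one test. When two outcomes both carry the primary label and no decision rule links them, a reader of the final report may treat significance on either as a positive trial, and the risk for that statement is above 5%. With no written order, the choice of which result to headline also stays open until the data are seen.

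The second primary test is not fully defined either. Section 5d says the change in each measure will be tested, and Section 4f (Study Procedures) describes eight PedsQL domains, but only emotional role limitation is powered. The post-wean assessment is 3 months after weaning in Sections 1, 4.d and 4f, and 6 months after discontinuation in Section 5d.

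**Working it through.** **Inputs.** From Section 5d: alpha 0.05 two-sided for each outcome; duration difference 36 days, SD 66, 98 per group; PedsQL difference 20 points, N = 130, 80% power, no SD. From the Table 2 caption: 85% completion, so 0.85 × 98 = 83.3 per arm. Assumed: the correlation between the two test statistics, 0 to 0.9.

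**1. Reproducing the plan's duration power.** The standardised difference is 36 / (66 × √(2/98)) = 36 / 9.43 = 3.82. Normal-approximation power is Φ(3.82 − 1.96) = 96.8% (noncentral t: 96.7%). This matches the stated 97%. The match uses all 98 per group. Applying the caption's 85% completion gives 94.1%, so results below are shown for both 83 and 98 per arm.

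**2. Chance of at least one false primary claim, if either success counts and neither effect is real.**

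- Independent tests: 1 − 0.95² = 9.75%.
- Upper limit for any dependence: 0.05 + 0.05 = 10%.
- Correlated tests: 1 − P(|Z₁| ≤ 1.96 and |Z₂| ≤ 1.96), with (Z₁, Z₂) bivariate normal:

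| Assumed correlation | Chance of at least one false claim |
|---|---|
| 0 | 9.75% |
| 0.3 | 9.51% |
| 0.5 | 9.07% |
| 0.7 | 8.35% |
| 0.9 | 7.04% |

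The value stays above 5% for every correlation below 1.

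**3. Duration power under a Bonferroni split (0.025 each), noncentral t, 36 days, SD 66.**

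| Per arm | Alpha 0.05 | Alpha 0.025 |
|---|---|---|
| 83 | 93.7% | 89.4% |
| 98 | 96.7% | 94.0% |

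**4. PedsQL power under the same split.** The SD has to be inferred. Reading 130 as the total (65 per arm), SD = 20 / [(1.960 + 0.842) × √(2/65)] = 40.7 points. Reading it as 130 per arm would need 260 infants, more than the 196 planned. Normal approximation, SD 40.7:

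| Per arm | Alpha 0.05 | Alpha 0.025 |
|---|---|---|
| 65 | 80.0% | 71.2% |
| 83.3 | 88.7% | 82.4% |
| 98 | 93.1% | 88.5% |

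The result depends on the SD. At alpha 0.025 with 83.3 per arm, power is 92.6% for SD 35, 83.8% for SD 40, 73.5% for SD 45 and 63.3% for SD 50.

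**The case against.** The strongest reply is that these are separate aims with separate hypotheses. If each hypothesis is claimed only on its own test, each claim keeps its 5% error rate, and whether two such aims need joint control is partly a matter of judgement. This stands to the extent that the inflation depends on a success rule the plan does not state. It does not remove the gap: both outcomes are labelled primary, both serve the single overall objective in Section 1, and no rule says how two results combine into a trial conclusion. If both had to succeed there would be no inflation, but the plan does not say that either.

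Three stronger conclusions that a reader might draw are not supported:

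- *The error rate is simply about 10%.* That is the independence value. Section 4.e calls duration the main driver of caregivers' emotional and financial health, which points to related outcomes and a somewhat lower figure.
- *The plan gives no indication of which outcome leads.* Several signals favour duration: it is listed first in Section 4.e, it is Aim 1 in Section 1, it is called the primary outcome in Section 5d, and the 98 per group appears in its power statement. Others point to quality of life. The signals conflict, and none makes one test conditional on the other. Because both outcomes are prespecified as primary, what stays open is emphasis, not promotion of a secondary outcome.
- *The error exceeds 10% because eight domains could be tested.* The plan does not say that any single domain would count as primary success, so no figure can be attached. The lack of a named score is a gap in definition.

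**Conclusion.** The concern holds in conditional form. The plan has two primary outcomes, each at two-sided 0.05, and no rule connecting them. If success on either counts, the chance of at least one false primary claim is 9.75% under independence and about 9.1% to 7.0% for correlations of 0.5 to 0.9. The correlation is an assumption, and the calculation takes PedsQL as one test, which the plan has yet to define. The design itself remains sound. This should be settled before analysis, and it needs no extra infants unless the PedsQL SD turns out well above the implied 40.7 points and a Bonferroni-type split is chosen.

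**What to change.** State one rule in Sections 4.e and 5d before analysis:

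- **Fixed sequence:** test duration first at two-sided 0.05, and PedsQL at two-sided 0.05 only if duration is significant; or
- **Holm** across the two outcomes.

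Under either rule, name one PedsQL score and one post-wean time point as the primary PedsQL test, reconciling the 3 months in Sections 1, 4.d and 4f with the 6 months in Section 5d. Treat the other domains as secondary. Otherwise the second step stays undefined, and several domains could each be tested at 0.05 once duration succeeds. Number the aims the same way in Sections 1 and 5d.

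**Cost.** This is a change of wording, apart from any change to the visit schedule if the 6-month time point is kept. The fixed sequence leaves duration power untouched, but PedsQL cannot be claimed as a confirmed primary result if duration fails. If the 36-day effect is real, that happens in about 100 − 93.7 = 6.3% of trials with 83 completers per arm. Holm lets either outcome succeed alone and does at least as well as the Bonferroni figures above: with 83 per arm, 89.4% for duration and about 82% for PedsQL; with 98, 94.0% and about 88.5%. The PedsQL figures assume that 130 is the total sample and that the SD is the 40.7 points this implies. The sponsor should state the SD actually used.
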